7.1.3 Study Treatments

Throughout the study, nivolumab, pembrolizumab and enfortumab (where applicable) will be administered in accordance with approved labeling. Nivolumab is to be administered by intravenous infusion, 240 mg Q2W or 480 mg Q4W. Guidance for adverse event management and associated nivolumab treatment modifications are provided in product labeling. Pembrolizumab is to be administered by intravenous infusion, 200 mg Q3W. Guidance for adverse event management and associated pembrolizumab treatment modifications are provided in product labeling. Enfortumab is to be administered by intravenous infusion, with a starting dose of 1.25mg/kg on days 1 and 8 of Q3W (a lower dose may be used if necessary; see **Error! Reference source not found.** of the protocol). In addition, a dose de-escalation step for enfortumab may be undertaken as appropriate. Guidance for adverse event management and associated enfortumab treatment modifications are provided in product labeling. Note: nivolumab (for Cohorts 1 through 8) or pembrolizumab (for Cohort 9) should be administered after sitravatinib (and specifically after the 30 minute PK sampling on applicable study visits), whereas enfortumab (for Cohort 9) should be administered at least 30 minutes after pembrolizumab.

Sitravatinib capsules will be administered orally. A starting dose of 120 mg QD of the free base capsule formulation (in 28-day cycles) was used for the sitravatinib and nivolumab combination cohorts under previous versions of this protocol. Newly enrolled patients under Cohorts 1 through 6 will continue to receive the free base formulation with the starting dose of 120 mg QD. For Cohorts 7 and 8, transition to use of an alternative formulation, sitravatinib malate capsule formulation, is being implemented with this protocol Version 4.0. Newly enrolled patients in Cohorts 7 and 8 under this protocol Version 4.0 will receive a starting dose of 100 mg QD of the malate capsule formulation (an equivalent dose to 120 mg QD of the free base capsule formulation), based on the results of Study 516-006 described in Section **Error! Reference source not found.** of the protocol. Patients who began treatment with the free base capsule formulation will remain on the free base capsule formulation throughout the duration of the study. A lead-in dose escalation will determine the starting dose of sitravatinib using the malate capsule formulation (21-day cycles) for sitravatinib combination with pembrolizumab and enfortumab Cohort 9. Guidelines for sitravatinib administration and dose reduction in the event of toxicity are provided in Section **Error! Reference source not found.** of the protocol.

Detailed descriptions of the study treatments are presented in Section 5 of the protocol.

7.1.4 Contingent PK Evaluation in Patients with Renal Impairment

In the event results in initial patient cohorts enrolled in this study or results emerging from other ongoing clinical trials of sitravatinib are of high interest for efficacy, the evaluation of the pharmacokinetics of sitravatinib in patients with mild or moderate renal impairment may be implemented. Appendix 7 of the protocol describes the plan for this assessment. Upon implementation of this study appendix, the evaluation of the PK of sitravatinib in at least 6 patients each having mild or moderate renal impairment at enrollment will be undertaken. Details of this analysis will be provided in the PKAP.

7.1.5 Hypothesis and Sample Size Considerations

This Phase 2 study will use Predictive Probability Designs (Lee-2008) for initial cohort 1 and 2. In summary, Cohorts 3 and 4 will also use Predictive Probability Designs with the same assumptions as the initial cohorts (Section 6.1), Cohorts 5 and 6 will use Predictive Probability Designs with revised assumptions, Cohorts 7 and 8 will use confidence interval method with the revised assumptions, the lead-in dose escalation portion of Cohort 9 will use the mTPI-2 design (Guo-2017; Appendix 2).

In creating the statistical designs, the Type 1 error (α) is constrained to <0.05 and Power ($1-\beta$) is constrained to ≥ 0.90 .

7.1.5.1 Cohort 1 and 2:

ORR in accordance with RECIST v1.1 is the primary endpoint. The ORR using nivolumab in the population of advanced/metastatic urothelial carcinoma who experienced disease progression on or after treatment with a checkpoint inhibitor is assumed to be 5% (p_0); thus, this rate is considered uninteresting. The target ORR using sitravatinib in combination with nivolumab in this study population is 30% (p_1). Stage 1 of enrollment will include a minimum of 9 evaluable patients in each cohort. Patients included in the evaluable population will have at least one on-study disease assessment prior to discontinuation; patients who discontinue treatment due to adverse events or withdrawal of consent prior to the first on-study disease assessment will not be included in the evaluable population. With exactly 9 evaluable patients at Stage 1, if at least 1 patient has an Objective Response, 8 additional evaluable patients will be enrolled in the treatment cohort, for a total sample size of 17 evaluable patients. If at least 3 Objective Responses are observed in a treatment cohort, further investigation may be warranted. If the true ORR is 5% (null hypothesis), the probability of early termination during the study is 0.63; the Type 1 error is equal to 0.0466 and the power is equal to 0.9045.

The exact stopping rules for futility for each cohort will be calculated based on the Predictive Probability Design, once the exact number of patients evaluable at Stage 1 is known. The aim is to include a minimum of 9 evaluable patients at Stage 1. If Stage 2 results in a cohort are of high interest for efficacy (in terms of examining the risk benefit ratio and not only in terms of ORR), enrollment may be expanded to as many as 40 patients total in that cohort to narrow the 95% CI around the ORR point estimate and to further characterize the durability of disease control.

Table 5 presents estimates of the 95% CI around the observed ORR for several potential outcomes using the sample size of 40 patients, and the Clopper-Pearson method.

Table 5 Estimates of 95% CI Using Clopper-Pearson in After Enrollment of 40 Patients

Number of Observed Responses Among 40 Patients	ORR	95% CI
10	25%	(12.7%, 41.2%)
12	30%	(16.6%, 46.5%)
14	35%	(20.6%, 51.7%)
16	40%	(24.9%, 56.7%)
20	50%	(33.8%, 66.2%)

7.1.5.2 Cohort 3 and 4:

In the event that results in the initial study cohorts are of high interest for efficacy, one or more cohorts in patients with documented disease progression on or after a PD-(L)1 checkpoint inhibitor therapy as the most recent treatment, and who previously received (in combination or separately) treatment with selected immunotherapies, including but not limited to anti-CTLA-4, anti-OX40 or anti-CD137 therapy, may be added to the study. Decisions for implementation of additional cohorts in the study will be made in collaboration with the Investigators and documented for Regulators and Institutional Review Boards by an Administrative Letter to Investigators.

Based on the evolving treatment landscape of urothelial carcinoma including regimens combining selected immunotherapies with checkpoint inhibitors, and in consult with Investigators, both Cohort 3 and Cohort 4 described in this appendix were implemented by an Administrative Letter dated January 2019.

The statistical design is the same as cohort 1 and 2.

7.1.5.3 Cohort 5 and 6:

In the event that results in the initial study cohorts are of high interest for efficacy, one or more cohorts in patients who have not previously received checkpoint inhibitor therapy (CIT-naïve) may be added to the study. Decisions for implementation of additional cohorts in the study will be made in collaboration with the Investigators and documented for Regulators and Institutional Review Boards by an Administrative Letter to Investigators.

Based on the evolving treatment landscape of urothelial carcinoma and early efficacy and safety results from active study cohorts, and in consult with Investigators, both Cohort 5 and Cohort 6 described in this section were implemented by an Administrative Letter dated May 2019.

The ORR using nivolumab in the population of advanced/metastatic urothelial carcinoma who have not previously received treatment with a checkpoint inhibitor therapy is assumed to be 20% (p_0); thus, this rate is considered uninteresting. The target ORR using sitravatinib in combination with nivolumab in this study population is 40% (p_1). Stage 1 of enrollment will include approximately 24 evaluable patients in each cohort. Patients included in the evaluable population will have received treatment with both sitravatinib and nivolumab and will have at least one on-study disease assessment prior to discontinuation; patients who discontinue treatment due to adverse events or withdrawal of consent prior to the first on-study disease assessment will not be included in the evaluable population. With exactly 24 evaluable patients at Stage 1, if at least 6 patients have Objective Responses, enrollment of 21 additional evaluable patients is needed in the treatment cohort, for a total sample size of 45 evaluable patients. If at least 14 Objective Responses are observed in a treatment cohort, further investigation may be warranted. If the true ORR is 20% (null hypothesis), the probability of early termination during the study is 0.66; the Type 1 error is equal to 0.0483 and the power is equal to 0.9001.

The exact stopping rules for futility for both cohorts will be calculated based on the Predictive Probability Design, once the exact number of patients evaluable at Stage 1 is known. The aim is to include approximately 24 evaluable patients at Stage 1. The Sponsor retains the option to take more than one look at the data when making decisions based on the PPD method to expand cohorts.

7.1.5.4 Cohort 7 and 8:

In the event that results in the initial study cohorts are of high interest for efficacy, one or more cohorts in patients with documented disease progression on or after a PD-(L)1 checkpoint inhibitor therapy and an antibody-drug conjugate (ADC; e.g. enfortumab vedotin, sacituzumab govitecan), in any order or in combination together. Decisions for implementation of additional cohorts in the study will be made in collaboration with the Investigators and documented for Regulators and Institutional Review Boards by an Administrative Letter to Investigators.

Based on the evolving treatment landscape of urothelial carcinoma in particular with the clinical activity of ADCs, and early efficacy and safety results from active study cohorts, and in consult with Investigators, both Cohort 7 and Cohort 8 described in this section were implemented by an Administrative Letter dated September 2019.

The ORR using taxanes in the population of advanced/metastatic urothelial carcinoma who have previously received treatment with a checkpoint inhibitor therapy and ADC is assumed to be 10%; thus, this rate is considered uninteresting. The design for Cohort 7 and Cohort 8 will utilize a 95% confidence interval to exclude an ORR of 10%. Assuming sitravatinib in combination with nivolumab treatment will result in an ORR of at least 25% in this treatment setting, a sample size of approximately 55 evaluable patients would be sufficient for the lower bound of a 2-sided 95% confidence interval (Clopper-Pearson method) to exclude an ORR of 10%.

The design will include a non-binding stopping rule for futility derived using East[®] software v6.5 to control the Type 2 error rate of 0.117. The Type 2 error spending function is based on the Rho family with parameter 2.0. The futility analysis will be conducted when approximately 17 evaluable patients (approximately 30% of the total number of patients) are available for the response assessment. The futility bound will be 1 or fewer observed responses among the first 17 patients.

7.1.5.5 Cohort 9:

In the event that results in the initial study cohorts are of high interest for efficacy, one or more cohorts in patients for treatment with sitravatinib in combination with pembrolizumab and enfortumab may be added to the study. Decisions for implementation of additional cohorts in the study will be made in collaboration with the Investigators and documented for Regulators and Institutional Review Boards by an Administrative Letter to Investigators.

Based on the evolving treatment landscape of urothelial carcinoma in particular with the clinical activity of ADCs, and early efficacy and safety results from active study cohorts, and in consult with Investigators, Cohort 9 described in this appendix is considered implemented of this protocol Version 4.0.

Study Design – Design details specific to Cohort 9 (including lead-in dose escalation) are described below including description of the populations to be enrolled into these contingent cohorts evaluating the triple combination of sitravatinib, pembrolizumab and enfortumab, the study design and dose-limiting toxicities (DLTs) as applicable.

Initially, the lead-in dose escalation portion of Cohort 9 will evaluate sitravatinib administered in combination with pembrolizumab and enfortumab in patients who have previously received a PD-(L)1 checkpoint inhibitor and a platinum-based chemotherapy. If a tolerable dose is identified for sitravatinib in combination with pembrolizumab and enfortumab, the recommended dose regimen of sitravatinib in combination with pembrolizumab and enfortumab may be further evaluated in as many as 2 populations including in patients who have previously received a PD-(L)1 checkpoint inhibitor. Depending on the results in previous cohorts, only one or more of Cohort 9 may be implemented. Description of the populations to be enrolled into Cohort 9 evaluating the triple combination of sitravatinib, pembrolizumab and enfortumab are described below.

Lead-In Dose Escalation Portion of Cohort 9 Evaluating Sitravatinib in Combination with Pembrolizumab and Enfortumab

This portion of the study will begin with the lead-in dose escalation portion of Cohort 9 of up to three dose levels of sitravatinib in combination with up to two dose levels of pembrolizumab and enfortumab combination regimen, in patients who have previously received a PD-(L)1 checkpoint inhibitor and a platinum-based chemotherapy. Sitravatinib starting dose levels using the malate formulation are shown in Table 6, whereas the starting doses for pembrolizumab and enfortumab are shown in Table 7. Dosing will begin at 35 mg QD of sitravatinib in combination with the recommended doses of pembrolizumab and

enfortumab combination regimen. This starting dose for sitravatinib represents three dose levels below the dose administered as a single agent and in combination (with nivolumab) Phase 2 and 3 trials. Dose Level 3 in Table 6 is the dose used in single agent and combination Phase 2 and 3 trials. The starting doses for pembrolizumab and enfortumab (labeled as Dose Level 1 in Table 7) represent the recommended doses from the EV-103 Phase 2 trial and the EV-302 Phase 3 trial of pembrolizumab and enfortumab used in combination (Rosenberg-2020; Hoimes-2019). It is of note that the EV-302 Phase 3 trial also uses these recommended doses of pembrolizumab and enfortumab in the triple combination investigation arm combining pembrolizumab and enfortumab with the platinum-chemotherapy agents cisplatin or carboplatin. In addition, a dose de-escalation step for enfortumab may be undertaken as appropriate (labeled as Dose Level -1 in Table 7). Throughout the study, pembrolizumab and enfortumab will be administered in accordance with approved labeling. Guidance for adverse event management and associated pembrolizumab treatment modifications are provided in product labeling.

Table 6 Sitravatinib Starting Dose Levels for Lead-In Dose Escalation Cohort 9 (Malate Formulation)

Sitravatinib Dose Level	Sitravatinib Daily Dose
1	35 mg PO QD
-2¹	50 mg PO QD
2	70 mg PO QD
3	100 mg PO QD

Abbreviations: PO = orally; QD = once daily.

- 1 The 50 mg dose level will be enrolled only if de-escalation is needed after assessment of the next higher dose level (70 mg).

Table 7 Pembrolizumab and Enfortumab Dose Levels

Combination Regimen Dose Level	Pembrolizumab¹	Enfortumab¹
-1 ²	200 mg IV Q3W	1 mg/kg IV on days 1 and 8 of Q3W
1	200 mg IV Q3W	1.25 mg/kg IV on days 1 and 8 of Q3W

Abbreviations: IV = intravenous; Q3W = every 3 weeks.

- 1 Pembrolizumab and enfortumab should be administered according to USPI and standard care.
- 2 The 1 mg/kg dose level of enfortumab will be enrolled only if de-escalation is needed after assessment of the next higher dose level (1.25 mg/kg).

Dose-Limiting Toxicities (DLTs) in Cycle 1 for the Lead-In Dose Escalation Portion of Cohort 9

DLTs are only defined for patients in the lead-in dose escalation portion of Cohort 9. The definition of DLT for the purpose of dose escalation decisions includes any of the following events considered to be causally related to treatment with sitravatinib in combination with pembrolizumab and enfortumab that occurs from Cycle 1 Day 1 through pre-dose Cycle 2 Day 1:

Hematological DLTs:

- Grade 4 neutropenia, if it lasts more than 7 days.
- ≥ Grade 3 febrile neutropenia.

- \geq Grade 3 neutropenia with significant clinical sequelae.
- Grade 4 thrombocytopenia.
- Grade 3 thrombocytopenia associated with clinically significant bleeding.
- Any requirement for a platelet transfusion.
- Grade 4 anemia unexplained by underlying disease.

Non-hematological DLTs:

- \geq Grade 4 infusion related reaction.
- Grade 3 infusion related reaction that does not resolve within 24 hours.
- Any \geq Grade 4 non-hematological toxicity.
- Grade 3 hypertension that cannot be controlled with medical therapy, including:
 - Severe hypertension with systolic blood pressure ≥ 180 mmHg or diastolic blood pressure ≥ 120 mmHg, on more than one occasion.
 - Sustained uncontrolled hypertension, with systolic blood pressure ≥ 160 mmHg (but < 180 mmHg) or diastolic blood pressure ≥ 100 mmHg (but < 120 mmHg) lasting for ≥ 14 days or causing treatment delay for ≥ 4 days.
- Other Grade 3 non-hematologic toxicity lasting for > 3 days despite optimal supportive care, with the following exceptions:
 - Endocrine disorder (thyroid, pituitary, and/or adrenal insufficiency) that can be effectively managed with hormone replacement therapy.
 - Fatigue that persists for ≤ 7 days.
 - Rash that resolves to Grade ≤ 1 within 3 weeks.
 - Tumor flare (defined as local pain, irritation, or rash localized at sites of known or suspected tumor).
- Grade 2 pneumonitis or colitis that does not resolve to \leq Grade 1 as indicated by symptoms within 3 days after onset of the event despite optimal medical management with or without corticosteroids.
- \geq Grade 3 non-hematological laboratory abnormalities with clinical consequences that do not resolve within 24 hours.
- ALT $> 3 \times$ ULN with bilirubin $> 2 \times$ ULN.
- Any other related toxic effect during the first 3 weeks may be assessed as a DLT if, upon review by the Investigators and Sponsor, it is agreed that the toxicity was of sufficient severity to be considered dose limiting.
- Any toxicity that requires suspension of sitravatinib for more than 1 week.

- A patient did not receive at least 1 dose of pembrolizumab and at least 2 doses of enfortumab up to and including Cycle 2 Day 1 due to tolerability issues (i.e., other related AEs not attributed as DLTs).

Patients from the lead-in dose escalation portion of Cohort 9 are considered DLT evaluable if they experience a DLT during the first cycle of treatment or if they clear the DLT period. Patients who received prohibited therapy during Cycle 1 (refer to Section **Error! Reference source not found.**), or who did not take at least 80% of the planned dose of sitravatinib, the 1 planned dose of pembrolizumab and 2 planned doses of enfortumab in Cycle 1 will be ineligible for DLT evaluation and will be replaced unless they experience a DLT event. Initially, at least 3 patients will be enrolled at each new dose level. The first patient to be treated at each new dose level will be observed for at least one week prior to enrollment of subsequent patients at that dose level. Decision making for dose escalation or de-escalation will be in accordance with the mTPI-2 method (Dose-Finding Spreadsheet presented in Appendix 2), and will be made in collaboration with the Investigators and documented for Regulators and Institutional Review Boards by an Administrative Letter to Investigators.

For the lead-in dose escalation evaluation, no dose reductions of any investigational product are allowed during Cycle 1.

Hypothesis and Sample Size

Lead-In Dose Escalation Evaluation for Sitravatinib in Combination with Pembrolizumab and Enfortumab (Cohort 9)

Up to 30 patients may be enrolled into the lead-in dose escalation portion of Cohort 9.

The mTPI-2 design (Guo-2017) will be employed in decision making of dose escalation within each regimen investigated. The mTPI-2 design is based on the following assumptions:

- the maximum tolerated dose (MTD) is the dose associated with probability of dose limiting toxicity in 30% of patients during the first treatment cycle; and
- the acceptable variance around the MTD is - 0.05 to + 0.03 (i.e., the region of the MTD is 25% to 33% incidence of dose limiting toxicity).

Refer to 02 of the protocol for the dose escalation decision table using the mTPI-2 method.

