9.1 Hypothesis and Sample Size

This Phase 2 study will use Predictive Probability Designs ([Lee-2008](#)) for initial Cohorts 1 and 2. The design, hypothesis and sample size considerations for the initial Cohorts 1 and 2 are described below. Refer to [Appendix 5](#), [Appendix 6](#), [Appendix 8](#) and [Appendix 9](#) for study design and statistical considerations applicable to all contingent Cohorts 3 through 10. In summary, Cohorts 3 and 4 will also use Predictive Probability Designs with the same assumptions as the initial cohorts ([Appendix 5](#)), Cohorts 5 and 6 will use Predictive Probability Designs with revised assumptions ([Appendix 6](#)), Cohorts 7 and 8

will use confidence interval method with the revised assumptions (Appendix 8), the lead-in dose escalation portion of Cohort 9 will use the mTPI-2 design (Guo-2017; Appendix 9), and the dose expansion portion of Cohort 9 and Cohort 10 will use Simon 2-stage optimal designs (Simon-1989; Appendix 9).

In creating the statistical designs for initial Cohorts 1 and 2, the Type 1 error (α) is constrained to <0.05 and Power ($1-\beta$) is constrained to ≥ 0.90 .

ORR in accordance with RECIST v1.1 is the primary endpoint. The ORR using nivolumab in the population of advanced/metastatic urothelial carcinoma who experienced disease progression on or after treatment with a checkpoint inhibitor is assumed to be 5% (p_0); thus this rate is considered uninteresting. The target ORR using sitravatinib in combination with nivolumab in this study population is 30% (p_1). Stage 1 of enrollment will include a minimum of 9 evaluable patients in each cohort. Patients included in the evaluable population will have at least one on-study disease assessment prior to discontinuation; patients who discontinue treatment due to adverse events or withdrawal of consent prior to the first on-study disease assessment will not be included in the evaluable population. With exactly 9 evaluable patients at Stage 1, if at least 1 patient has an Objective Response, 8 additional evaluable patients will be enrolled in the treatment cohort, for a total sample size of 17 evaluable patients. If at least 3 Objective Responses are observed in a treatment cohort, further investigation may be warranted. If the true ORR is 5% (null hypothesis), the probability of early termination during the study is 0.63; the Type 1 error is equal to 0.0466 and the power is equal to 0.9045.

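### SAP 7.1.5 states power of at least 0.90 with no cohort limit, but the Cohort 7/8 confidence-interval design has 0.883 by its own Type 2 error and about 0.845 by exact calculation.

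*SAP*

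**What the plan says.** SAP 7.1.5 opens by naming the design used in each group of cohorts. For the post-ADC cohorts it says "Cohorts 7 and 8 will use confidence interval method with the revised assumptions". The next paragraph begins "In creating the statistical designs, the Type 1 error" and holds that error below 0.05 and power at or above 0.90. It names no cohorts. In Protocol 9.1 the matching sentence begins "In creating the statistical designs for initial Cohorts 1 and 2, the Type 1 error", and the protocol synopsis also attaches the constraint to the initial cohorts.

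SAP 7.1.5.4 gives the Cohort 7/8 design itself. The response rate with taxanes in patients "who have previously received treatment with a checkpoint inhibitor therapy and ADC is assumed to be 10" per cent. The combination is assumed to give a rate that "will result in an ORR of at least 25% in this treatment setting". The criterion is "The design for Cohort 7 and Cohort 8 will utilize a 95% confidence interval to exclude an ORR of 10" per cent, and "a sample size of approximately 55 evaluable patients would be sufficient for the lower bound of a 2-sided 95% confidence interval (Clopper-Pearson method") to exclude that rate. A non-binding futility rule stops at 1 or fewer responses among the first 17 patients and is described as derived "to control the Type 2 error rate of 0.117". Protocol Appendix 8 carries the same design. Neither document gives a minimum number of responses for success in Cohorts 7 and 8.

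**The concern.** Read in sequence, the SAP attributes power of at least 0.90 to every design it has just listed, Cohorts 7 and 8 included. Four paragraphs of cohort detail later it gives those cohorts a Type 2 error that implies less. Both statements cannot be true of the same design.

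What is at stake is the description of the design. A report that quotes the general sentence would credit Cohorts 7 and 8 with a power they lack. A negative result there would then look more informative than it is. The general sentence also sets cohorts side by side that use different evidence levels: the Type 1 errors quoted for Cohorts 1 to 6 are upper-tail values close to 5%, while a two-sided 95% interval corresponds to an upper-tail level of 2.5%.

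**Working it through.** **Inputs (SAP 7.1.5 and 7.1.5.4).** Null rate p0 = 0.10; target p1 = 0.25; n = 55 evaluable; two-sided 95% Clopper-Pearson interval, so upper-tail level 0.025; stated Type 2 error 0.117; non-binding stop at 1 or fewer of 17; Rho-family spending with parameter 2.

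**1. Which sense of Type 1 error the SAP uses.** For a two-stage rule that continues if more than f of n1 respond and succeeds with at least r of n:

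P(success | p) = sum over x > f of P(X1 = x | n1, p) × P(X2 ≥ r − x | n − n1, p).

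- Cohorts 1 to 4 (n1 = 9, f = 0, n = 17, r = 3): 0.0466 at 5% and 0.9045 at 30%, as stated.
- Cohorts 5 and 6 (n1 = 24, f = 5, n = 45, r = 14): 0.0483 at 20% and 0.9001 at 40%, as stated.

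These are upper-tail probabilities, and both designs satisfy the general sentence.

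**2. The stated figure for Cohorts 7 and 8.** Power = 1 − 0.117 = 0.883, already below 0.90.

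**3. Where 0.117 can come from.** Normal approximation with the null variance at the critical value:

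- critical proportion = 0.10 + 1.96 × √(0.10 × 0.90 / 55) = 0.10 + 1.96 × 0.0405 = 0.1793
- fixed-sample power = Φ[(0.25 − 0.1793) / √(0.25 × 0.75 / 55)] = Φ(0.0707 / 0.0584) = Φ(1.21) = 0.887
- adding one look at 17 of 55 that spends 0.117 × (17/55)² = 0.0112 of the Type 2 error (bivariate normal, correlation √(17/55)) gives Type 2 error 0.1172.

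This matches 0.117. A normal approximation at upper-tail 0.05, with the stop placed at 1.5 of 17, gives 0.1167 and rounds the same way, so the exact route is not certain. Neither version is the Clopper-Pearson rule.

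**4. The rule the SAP names, exactly.** The lower bound L at x of n solves P(X ≥ x | n, L) = 0.025. It therefore lies above 10% exactly when P(X ≥ x | n, 0.10) is below 0.025.

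| Responses of 55 | 95% lower bound | P(X ≥ x) at 10% | P(X ≥ x) at 25% |
|---|---|---|---|
| 10 (18.2%) | 9.08% | 0.0444 | 0.911 |
| 11 (20.0%) | 10.43% | 0.0189 | 0.845 |

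The cut-off is 11: one-sided Type 1 error 0.0189, power 0.845, Type 2 error 0.155.

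**5. With the futility stop followed.** Using the formula in step 1 with n1 = 17, f = 1, n = 55 and r = 11: Type 1 error 0.0177, power 0.821, Type 2 error 0.179.

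**6. Whether the approximate n of 55 rescues it.** Recomputing the cut-off at each n from 50 to 61, exact power under the interval rule without the stop peaks at 0.876 (n = 57, cut-off 11). The smallest n reaching 0.90 is 64 (cut-off 12, power 0.9065).

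**The case against.** The best defence is that this is a lost qualifier and no more. The SAP says it supplements the protocol and is to be read with it, and the protocol ties the constraint to the initial cohorts. The list before the sentence includes the mTPI-2 dose-finding design, which has no error and power pair of this kind, so a literal all-cohort reading is strained. SAP 7.1.5.4 openly gives the two-sided interval and the 0.117. Much of this stands. The cause is very probably the dropped words, the Type 1 error half of the constraint is met with room, and 0.117 is not a slip of arithmetic because a normal approximation returns it. It remains that the SAP sentence is untrue of a design named just before it, and that 0.117 understates the Type 2 error of the exact rule.

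A reader might also infer that 10 of 55 passes under one SAP statement and fails under the other. The documents do not support that. The general sentence describes how designs were built; it is not a success rule. The interval is the only success criterion for these cohorts, and 10 of 55 fails it at 9.08%. A two-sided exact test there gives p = 0.066.

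Nor is 10 the one cut-off that satisfies both constraints. That holds only if the futility look is ignored (0.0444 and 0.911). With the stop followed, a cut-off of 9 has Type 1 error 0.082, 10 has power 0.880 and 11 has power 0.821, so no cut-off satisfies both. The figures quoted for Cohorts 1 to 6 do count early stopping, so this is the like-for-like comparison.

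**Conclusion.** The point holds as a misstatement of power. For Cohorts 7 and 8 the SAP's general sentence promises at least 0.90. The design has 0.883 on its own stated Type 2 error, 0.845 on the exact rule, and 0.821 if the futility stop is followed. The shortfalls against 0.90 are 1.7, 5.5 and 7.9 percentage points. The Type 1 error limit is met.

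The exact figures assume exactly 55 evaluable patients, true rates of exactly 10% and 25%, and success defined as the Clopper-Pearson lower bound lying above 10%. Power is higher if the true rate exceeds 25%. The cut-off and power shift with the final denominator, which may differ from 55 because the size is approximate and SAP 11.6.1 runs the primary ORR analysis in the Full Analysis Population. Nothing here shows the success criterion to be ambiguous or the sample size to be invalid.

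**What to change.** In SAP 7.1.5, limit the Type 1 error and power sentence to the Predictive Probability Design cohorts (1 to 6), whose stated figures satisfy it. Limiting it to Cohorts 1 and 2, as Protocol 9.1 does, would also serve.

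In SAP 7.1.5.4, state that:
- the two-sided 95% Clopper-Pearson criterion governs, which is a one-sided 2.5% level;
- at exactly 55 evaluable patients it needs at least 11 responses, with the cut-off recomputed if the final number differs;
- exact power at a true ORR of 25% is about 0.845, or 0.821 if the futility stop is followed, in place of the power implied by 0.117.

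Keep the rule and the sample size as they are. The cost is a few sentences of SAP wording before database lock and a less favourable stated power. No patients, data or analyses are added.
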